### 10.3 Exploratory Study Endpoints

#### 10.3.1 Radiomic signatures extracted from MP-MRI prostate exam

The MP-MRI prostate exam is composed of three modalities which represent anatomy, cellularity and blood flow. *The contiguous regions across a modality based on a given criterion are referred to as habitats.* Here we propose a computational method to connect three modalities (T2, DWI and DCE) to find regions of interest that will characterize the prostate beyond the tumor location. The three modalities are registered with MIM Software which provides high level of accuracy of alignment. Two Regions of Interest (ROIs): Prostate and Peripheral Zone (PZ) are manually contoured in MIM. The pixels within the prostate are classified in three groups based on the distribution of the pixel intensity. In our approach, the subpopulation obtained by the categorization will be called high, low and uncertain with respect to the pixel intensities. Prostate biopsies will be placed in reference to the dominant and non-dominant SlmTVs identified. The biopsy histopathologic results (i.e., percent core tumor tissue, Gleason score and percent Gleason grade 4) will then inform us on the relevance of the habitat(s).

#### 10.3.2 Genomic signatures extracted from biopsy

493 genes in 16 pathways that include apoptosis, base excision repair, DNA double strand break repair, homologous recombination, mismatch repair, non-

homologous end joining, hypoxia, p53 signaling, prostate cancer signaling, androgen receptor signaling, and cell cycle checkpoint (including G1/S, G2/M & mitotic spindle checkpoint) will be assessed using a 1.4 million feature oligonucleotide microarray by GenomeDx as discussed above. Some of these pathways might also be useful in determining response to treatment and it would be beneficial to understand the timing of gene expression changes occur during the AS period and how such changes relate to alterations in imaging features. We will develop a predictive model including 493 genes in 16 pathways.

#### *10.3.3 Area under ROC curves as predictive measure and incremental prediction improvement for progression on baseline biopsy.*

Patients will be categorized at baseline by NCCN risk class ranging from very low risk to intermediate risk and into those who progressed on the baseline biopsy and those who did not. Logistic regression will be used to model the association between NCCN risk class and progression using AUC for ROC curves. The incremental benefit of mpMRI, genomic testing and molecular markers compared to NCCN risk alone will be evaluated by comparing AUC using a likelihood ratio test. MRI will be categorized from 1-5 using PIRADS, while genomic test scores and molecular markers can be used as continuous scores or categorized into levels of risk (low/ intermediate/high).

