#### 1.4.4 Biomarker Validation for Active Surveillance

Biomarkers, be they from blood, urine or tissue, have the potential to contribute meaningfully to the decision of whether to recommend treatment or AS, and perhaps when to convert to treatment for men undergoing AS. The most promising of these biomarkers include genomic signature panels that can be tested on biopsy tissue to provide important information on risk stratification and prognosis. Previous validations of these tissue markers have been performed using biopsy tissue from random sampling of the prostate. However, we plan to examine tissue biomarkers in two unique methods that may allow for a more enhanced prediction. First, we will be testing tissue

attained from MRI-US-guided biopsies, which will sample suspicious regions of the prostate most likely to harbor the dominant tumor. To the best of our knowledge, there have been no publications on biomarker assessment using tissue obtained from targeted biopsy. Biomarker testing from these tissue cores will be compared to cores from segmental sampling of the prostate to assess for any differences in risk assessment. Secondly, these biomarkers will be attained serially to assess the change over time in genomic risk assessment.

We have previously collaborated with GenomeDx who has developed techniques for the analysis of RNA-based gene expression in formalin fixed paraffin embedded (FFPE) tissues from prostate biopsy. Using their system, gene expression profiling will be performed using a high-density 1.4 million-feature expression microarray. Although previous genomic signatures have been limited in assessing risk among patients on active surveillance this study allows us to explore various combinations of genetic alterations seen in the tumor region most likely to be driving progression. Therefore, we can expand on previous findings and facilitate the development of other genomic alterations that may have more significant prognostic implications. We believe that the radiomic and genomic characterization of various regions within the prostate will complement each other as well as the histological assessment to help select patients who are likely to harbor tumors that will portend an unfavorable outcome on active surveillance.

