#### **3.3 Exploratory Objectives**

- 1) To define radiomic signatures on multiparametric MRI that select regions of the prostate that are likely to harbor more aggressive disease.
- 2) To molecularly characterize tissue from the multiparametric habitat-directed prostate biopsies and develop genomic signatures of indolent versus progressing prostate cancer using a 1.4 million feature oligonucleotide microarray capable of global high throughput analysis of formalin fixed paraffin embedded specimens.
- 3) To relate radiomics and genomics signatures to existing urine, serum and tissue biomarkers that have been associated with prostate cancer diagnosis and/or progression.
- 4) To determine the incremental benefit of mpMRI, genomic risk testing, and molecular markers at baseline compared to NCCN risk class for predicting reclassification on confirmatory baseline biopsy.
- 5) To evaluate serial changes in mpMRI, genomic risk scores and molecular markers and relate them to progression on active surveillance.

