# 7. CLINICAL, RADIOLOGICAL AND LABORATORY EVALUATIONS

## 7.1 Screening Evaluations

- History and physical exam, within 12 months prior to protocol enrollment.
- Serum PSA (+/-) 3 months of protocol enrollment.
- Pathology review at the University of Miami of the outside biopsy material, prior to enrollment.

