### **7.6 Biopsy Tissue Handling**

Immediately following each biopsy core, the tissues will be fixed in 10% formalin per routine. The formalin fixed tissues will be delivered to the Department of Pathology for paraffin embedding and sectioning.

The biopsies are to be placed in the tissue processor and processed routinely, and embedded in paraffin. Biopsies will be reviewed by a pathologist and the results (Gleason scoring and percent of tumor tissue) recorded in the patient's record per routine. The remainder of the block will be stored per institutional policy in the Department of Pathology and requests for the biomarker analyses made at a time batched staining is possible (after a number of cases have been accrued).

When the tissue is sectioned for biomarker analyses, the slides will be labeled with a research ID number and will not contain patient information. Biomarker data will be entered into the Active Surveillance Database, which links the patient Medical Record number to a participant's Research ID number and in which data on each patient related to biopsies and treatments will be recorded. De-identified data will be sent to Genome Dx for gene expression profiling as described below.

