#### *10.3.4 Serial changes in markers related to progression*

mpMRI, genomic scores and molecular marker scores will be assess and associated to the risk of progression on trial using mixed model repeated measures adjusted for relevant demographic and clinical factors.

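### In Section 10.3.3 the baseline genomic score appears to come from the biopsy that defines reclassification, so its AUC gain over NCCN class would be a concurrent association, not prediction

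*Combined protocol and SAP*

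**What the plan says.** Exploratory objective 4 (Section 3.3) concerns the added value of mpMRI, "genomic risk testing, and molecular markers at baseline compared to NCCN risk class for predicting reclassification on confirmatory baseline biopsy". Section 10.3.3 carries this out. Men are classed at baseline by NCCN risk and divided "into those who progressed on the baseline biopsy and those who did not". Logistic regression and AUC then measure what mpMRI, genomic testing and molecular markers add to NCCN class.

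On the tissue, Section 1.4.4 says that testing will use material "attained from MRI-US-guided biopsies, which will sample suspicious regions of the prostate most likely to harbor the dominant tumor". It adds: "Biomarker testing from these tissue cores will be compared to cores from segmental sampling of the prostate to assess for any differences in risk assessment". On timing it says: "Secondly, these biomarkers will be attained serially to assess the change over time in genomic risk assessment". In Section 7.6 the pathologist reads each biopsy, the rest of the block is stored, and biomarker requests wait until cases can be batched. The section ends: "De-identified data will be sent to Genome Dx for gene expression profiling as described below". For the pre-enrolment biopsy, Section 7.1 lists only "Pathology review at the University of Miami of the outside biopsy material, prior to enrollment".

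Section 10.3.4 says that mpMRI, genomic and molecular scores "will be assess and associated to the risk of progression on trial using mixed model repeated measures". It states no lag between score and outcome.

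**The concern.** A predictor has to be available before the outcome that it predicts. If the genomic score is run on cores from the initial protocol biopsy, it cannot be known before that biopsy is taken. Under Section 7.6 it would be produced after the histology has been read. The comparator, NCCN class, is a baseline category that I take to be assigned from enrolment data, without protocol-biopsy tissue. The AUC comparison would then set a pre-biopsy variable against a measurement made on the outcome specimen.

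A score that merely tracks grade in the sampled cores would appear to add to NCCN class even if it could not tell, before biopsy, which men would be reclassified. The stated rationale for the biomarkers is to help select men for surveillance, so a result labelled as prediction could be read as supporting a use that the analysis had not tested.

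**Working it through.** **Plan's own figure.** No AUC, sample size or power is stated for Section 10.3.3 or 10.3.4. The one power figure belongs to the primary endpoint (Section 10.4): 97.3% with 150 patients, 12.5% against 25%, two-sided 5%. It reproduces. An exact binomial test with upper tail at most 0.025 rejects at 28 or more of 150, with null tail 0.0193 and power 0.9734. Nothing below changes it.

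**Tracing the specimen.**
1. Genomic tissue: protocol MRI-US biopsy cores, targeted and segmental, repeated at successive biopsies (Sections 1.4.4 and 7.6).
2. Diagnostic biopsy: eligibility and pathology review (Sections 6.1 and 7.1, Appendix II). No section sends it for expression profiling.
3. Outcome in 10.3.3: the result of the baseline protocol biopsy.
4. From 1 to 3, predictor and outcome appear to share one specimen.
5. mpMRI, blood and urine are not biopsy tissue (Sections 7.2, 7.4 and 7.7), so step 4 applies to the genomic score only.

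**Illustration A (assumed effect sizes).** For two normal distributions d SD apart, AUC = Φ(d/√2).
- d = 0.5: Φ(0.354) = 0.638
- d = 1.0: Φ(0.707) = 0.760
- d = 1.5: Φ(1.061) = 0.856

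**Illustration B (assumed correlations, simulated).** Let b be the grade of the baseline tissue and d the grade of the diagnostic tissue, both standard normal with correlation 0 to 0.4. The score is k × grade + √(1 − k²) × noise, so it holds nothing beyond the grade of the tissue it is run on. Reclassification is the top 7% or 25% of b. The 7% is the historical first re-biopsy progression in Section 1.5.1. The 25% is the 24-month planning rate in Section 10.4, used here as a high end.

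| k | AUC, score on the baseline cores | AUC, same score on diagnostic tissue |
|---|---|---|
| 0.3 | 0.642 to 0.677 | 0.499 to 0.569 |
| 0.5 | 0.740 to 0.786 | 0.500 to 0.612 |
| 0.7 | 0.841 to 0.885 | 0.498 to 0.655 |

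Both illustrations give stand-alone AUCs, not increments over NCCN class.

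**Section 10.3.4.** Biopsies are planned at baseline, 12, 24 and 36 months. A score from biopsy k−1 exists for the outcomes at 12, 24 and 36 months. A change that ends at biopsy k−1 needs two earlier biopsies, so it exists only for the 24- and 36-month outcomes. A man who progresses at 12 months has only the 0-to-12-month change, which uses the biopsy that defined his event.

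**The case against.** The strongest reply is that Section 10.3.3 does not name the tissue. Outside biopsy material reaches the institution for review before enrolment, and no section rules out profiling it. That stands: the shared specimen is an inference. It is nevertheless the only reading that the documents describe, and if diagnostic tissue is intended the plan has to say so.

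A reader might infer that the score and the outcome are the same thing, so that the analysis is strictly circular. The documents do not support this. Expression and Gleason grade are different measurements. Progression in Section 10.1.1 also includes patient-level core counts and treatment regardless of histology, which a score from one core does not determine. The defect is concurrency within a specimen, not identity.

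A reader might also infer that Section 10.3.4 is circular as written. It claims association only, with no AUC and no incremental benefit, and it states no timing. The problem would arise only if the score from the progressing biopsy were used to speak of risk. Scores from earlier biopsies are valid predictors of later progression.

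Finally, the AUC values rest wholly on assumed inputs and are not increments, so they cannot be read as the bias expected in this trial. That also stands.

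**Conclusion.** The point holds for the genomic part of exploratory objective 4 and Section 10.3.3. As the plan is written, a score that appears to come from the baseline biopsy would be credited with predicting that biopsy's result. This rests on the inference that baseline genomic tissue is protocol-biopsy tissue, and on NCCN class being known before the biopsy. For Section 10.3.4 it holds only as an unstated time order that needs to be fixed.

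The size cannot be estimated from the documents. The values of 0.64 to 0.86 show what assumed differences of 0.5 to 1.5 SD would produce. Illustration B shows that the same score could give 0.64 to 0.89 on the outcome tissue and 0.50 to 0.66 on earlier tissue, again on assumptions. mpMRI and fluid markers, the primary endpoint and its 97.3% power are not affected.

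**What to change.** - **Section 10.3.3 and exploratory objective 4:** state which tissue the genomic score comes from. Limit the predictive AUC comparison with NCCN class to predictors available before the baseline biopsy. The windows in Section 7.2 for imaging, fluids and biopsy overlap, so check collection dates.
- **Score from the baseline biopsy:** report it only as a concurrent association with histology, which Section 10.5 already plans. It may stay in the predictive comparison if it is run on pre-enrolment diagnostic tissue.
- **Section 10.3.4:** for any statement about risk of progression at biopsy k, use the score from biopsy k−1. Label same-visit associations as concurrent.

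Relabelling costs only text: one exploratory comparison changes its name. The first biopsy has no lagged genomic score, and lagged change is confined to the 24- and 36-month outcomes. Using diagnostic tissue costs more, because outside blocks up to 18 months old at enrolment (Section 6.1) would have to be retrieved and assayed, and some may not be available.

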#### *10.3.4 Serial changes in markers related to progression*

mpMRI, genomic scores and molecular marker scores will be assess and associated to the risk of progression on trial using mixed model repeated measures adjusted for relevant demographic and clinical factors.

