## 7.2 Evaluations During Intervention\*

- Multiparametric MRI obtained at the University of Miami (+/-) 3 months of enrollment and at 12, 24, and 36 months from initial protocol prostate biopsy.

- MRIus-guided biopsies will be obtained at 0 to 3 months from enrollment (“initial biopsy”) and at 12, 24 and 36 month from initial biopsy.
- History and physical at the discretion of the treating physician. Treating physician can be outside of UM..
- Serum PSA will be done preferably every 6 months or at least once a year up to 36 months from the initial biopsy. If the subject progress, PSA should be done every 6 months (+/- 3 months) or at the discretion of the clinician for the first 3 years and then annually thereafter (+/-6 months) for up to 5 years post treatment.
- If possible, plasma and/or serum (up to 5 tubes) for research purposes (biomarkers) may be obtained at 0 to 3 months from enrollment and at 12, 24, and 36 months from initial biopsy (optional - patient may refuse),
- If possible, post prostate-massage urine (approximately 50 mL) may be collected for research purposes at 0 to 3 months from enrollment and at 12, 24, and 36 months from initial biopsy (optional - patient may refuse). Urine research collection will not be done if research funds are not available.
- Quality of Life surveys obtained 0 to 3 months after enrollment and every 12 months from initial biopsy:
  - Expanded Prostate Cancer Index Composite Questionnaire (EPIC+SF12)
  - Memorial Anxiety Scale for Prostate Cancer patients (MAX-PC)
  - Optional - Food Frequency Questionnaire (FFQ) will be collected only atbaseline.

*\* Follow-up evaluations and visits may occur  $\pm$  1.5 months around each scheduled 6-month timepoint. For example, for the 6 month follow-up, the patient may be seen anytime between 4.5 and 7.5 months from the time of the first prostate biopsy. For the 12-month follow-up, the patient may be biopsied between 10.5 and 13.5 months from the time of the first prostate biopsy. Since the first biopsy may be from between 0-6 months from the day the patient is enrolled, each subsequent calendar event is timed in reference to the time of that first biopsy.*

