### 7.3 Early discontinuation of study participation

Patients who experience protocol-defined progression will have attained the primary study outcome and will undergo treatment either with radical prostatectomy or whole gland image guided radiotherapy of the prostate at the University of Miami. Their histopathology (for surgery patients) and rates of biochemical recurrence will be followed and compared to historical series for comparison with cohorts not undergoing MRI guided selection for surveillance versus immediate treatment. However, those who refuse the recommendation for treatment will continue to be followed per active surveillance standard of care guidelines. Furthermore, those who seek treatment outside UM will be contacted for information on histopathology (for those undergoing surgery) and rates of biochemical recurrence. Patient refusal of the recommendation for treatment or further follow-up beyond progression will not be a protocol deviation. Patients who are without progression upon completion of the third annual biopsy will be censored without progression.

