## **7.7 Molecular Analyses of Blood and Urine**

The objectives are to identify and examine molecular and genomic biomarkers in blood products and the urine that predict for disease progression and see how they correlate with radiomic and genomic signatures from distinct regions of the prostate.

Blood may be collected at baseline, and at 12, 24 and 36 months after initial biopsy. Urine post prostate massage may be collected at baseline and 12, 1,24 and 36 months after initial biopsy. Note that the collection of research fluids is optional – the patient can refuse the procedure. While these are exploratory studies, of key importance is to have such samples collected prospectively on a well-defined group of patients. Any urine or blood that is not used for specific biomarker testing will be stored for biomarkers development or validation.

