receiver's operating characteristic curve (AUC) with 10-fold cross-validation approach to evaluate performance of prediction model. Radiomic profiles on multi-parametric MRI that suggest regions of the prostate that are suspicious for more aggressive prostate cancer will be correlated to histopathologic findings from biopsy of these regions. Genomic profiles from tissue cores in each region will be correlated to radiomic profiles and histopathology from that region to see what each adds to improving the ability to predict patients who are likely to harbor more aggressive tumors that would portend poor outcome on active surveillance. Radiomic and genomic profiles from MRI targeted biopsies will be compared to segmental biopsies to see if profiles from targeted biopsies are more informative for risk assessment compared to segmental biopsy using longitudinal analysis approach. We will also assess how these profiles change over time in serial imaging and biopsy and see if/ how these profile changes correlate to change in histopathology. We will also relate genomic and radiomic profiles of the prostate to common serum and urinary markers that have been used predict progression on active surveillance. For continuous outcomes, association between outcome and other covariates will be examined using linear regression model and correlation coefficient. For binary outcomes and time-to-event outcomes, logistic regression and Cox proportional hazards regression will be used, respectively. All tests will be two-sided and statistical significance will be considered when  $p < .05$  after multiplicity adjustment.

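### Section 10.3.4 addresses risk of progression with a repeated-measures model that yields no risk, and nothing lags or excludes the marker taken at the progression visit

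*Combined protocol and SAP*

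**What the plan says.** The analysis serves the fifth exploratory objective in Section 3.3: "To evaluate serial changes in mpMRI, genomic risk scores and molecular markers and relate them to progression on active surveillance". Section 10.3.4 gives its method in one sentence: the scores will be "associated to the risk of progression on trial using mixed model repeated measures adjusted for relevant demographic and clinical factors". It does not name the response variable, the effect to be tested or the visits that enter.

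Four other places bear on it.

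- **Timing.** Section 7.2 states "MRIus-guided biopsies will be obtained at 0 to 3 months from enrollment", then repeats the biopsy at 12, 24 and 36 months from the initial one. MRI is obtained around enrollment and "at 12, 24, and 36 months from initial protocol prostate biopsy". Section 7.7 adds "Blood may be collected at baseline, and at 12, 24 and 36 months after initial biopsy", with urine on the same annual pattern, and the study calendar in Appendix II agrees. Blood and urine are optional.
- **Source of the genomic score.** Sections 1.4.4 and 7.6 take it from the study biopsy tissue, serially.
- **End of the series.** Section 7.3: "Patients who experience protocol-defined progression will have attained the primary study outcome and will undergo treatment".
- **Other models.** Section 10.5 says "For binary outcomes and time-to-event outcomes, logistic regression and Cox proportional hazards regression will be used, respectively". Of the radiomic and genomic profiles it says "We will also assess how these profiles change over time in serial imaging and biopsy", and it plans to correlate those changes with changes in histopathology.

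**The concern.** A mixed model for repeated measures describes the marker. Progression can enter it only as a label, which for each man is known only after his later biopsies. The result is a difference in mean level or trajectory between men who do and do not eventually progress. It is neither a hazard nor a probability of progression, so it does not answer the question that Section 10.3.4 poses.

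The second problem is which values enter. A progressor's series normally ends at the biopsy that shows progression, so his last marker value comes from the same visit and, for genomics, from the specimen that decides the event. With no rule on that value, the default is to include it. A marker that merely reads high when higher-grade tissue is sampled would then separate the groups.

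This matters because the plan wants prediction. Section 1.4.4 hopes that biomarkers may inform when a man on surveillance should convert to treatment, and Section 7.7 seeks markers that predict progression. A same-visit association reported as risk would be misread for those uses.

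**Working it through.** **The plan's own figure.** Section 10.4 gives one power figure, 97.3%, for the primary binomial test (12.5% against 25%, 150 men, two-sided 5%). The exact test rejects at 28 or more, or 10 or fewer, of 150, and its power at 25% is 97.34%. The figure reproduces, but it concerns a different analysis. Section 10.3.4 states no figure.

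**Inputs.** From the documents: 150 men and 25% cumulative progression at 24 months (10.4), counted at the third of four biopsies (10.5). Assumed, because the documents are silent: marker shift d, within-man correlation ρ, and the split of progression across biopsies. Three splits were used, each giving about 25% by the third biopsy:

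- equal, 9.14% per biopsy: 1 − 0.9086³ = 0.250
- none at the initial biopsy, then 13.4%: 1 − 0.866² = 0.250
- front-loaded, 15/7/5/3%: 1 − 0.85 × 0.93 × 0.95 = 0.249

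**Model.** Marker = random intercept (variance ρ) + error (variance 1 − ρ) + d at the progression visit only. Before that visit the marker carries no information on progression. The mixed model adjusts for visit, with exchangeable covariance, and tests at an unadjusted 5%; 600 to 1,000 simulated trials per cell.

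**Rejection with the progression-visit value included** (150 men, d = 0.5 to 0.8 SD, ρ = 0.3 to 0.7):

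| Split | Progressor main effect | Progressor × linear time | Progressor × visit |
|---|---|---|---|
| Equal | 41-85% | 32-99% | 26-97% |
| None at initial | 27-72% | 58-100% | 43-100% |
| Front-loaded | 55-92% | 14-84% | 11-75% |

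With d = 0.3 SD the range is 9-56%; with no shift, 3.7-6.8%. With 207 to 230 men (the accrual goal of 230, and 230 × 0.9 = 207 after 10% dropout) and d = 0.5 to 0.8 SD, it is 13-100%. A further split of 10/8/9.4/7% with ρ = 0.5 gave, for progression by time, 46% at 0.5 SD and 93-95% at 1.0 SD in two separate runs.

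**What removes the effect:**

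- mixed model without the progression-visit value: 3.5-7.2% in every scenario run
- discrete-time logistic hazard model, marker lagged one visit (equal split, d = 0 to 0.8 SD, ρ = 0.5 and 0.7): 3.7-5.7%
- the same hazard model with the same-visit marker: about 90% at 0.5 SD and 100% at 0.8 SD

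The Monte Carlo standard error at 5% with 600 trials is √(0.05 × 0.95 / 600) = 0.9 points. The choice of visit drives the rejections; changing the model class alone does not cure them.

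**Events left after lagging**, under 10/8/9.4/7% (1 − 0.90 × 0.92 × 0.906 = 0.250 by the third biopsy):

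- biopsy 1: 150 × 0.10 = 15.0
- biopsy 2: 135 × 0.08 = 10.8
- biopsy 3: 124.2 × 0.094 = 11.7
- biopsy 4: 112.5 × 0.07 = 7.9

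The total is about 45. A lagged level needs one earlier value: 10.8 + 11.7 + 7.9, about 30 events. A lagged change needs two: 11.7 + 7.9, about 20.

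**The case against.** The strongest reply is that these rejections are not errors for the stated objective. Section 3.3 asks only to relate serial changes to progression, and Section 10.5 makes concurrent change an aim. A marker that shifts when progression is found is associated with progression, so the percentages are power to detect that association. This stands: the result misleads only if read as prior risk or lead time. But Section 10.3.4 uses the word risk, Sections 1.4.4 and 7.7 show that prediction is wanted, and Section 10.5 already covers the concurrent question.

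Four stronger readings might be inferred, and the documents do not support them.

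- *The plan prescribes use of the progression-visit value.* It does not. This follows from coinciding schedules and the absence of a rule. For MRI the objection is weaker still, because Section 7.5.1 has the scan read before the biopsy that it guides.
- *The plan has no model for risk.* Section 10.5 names logistic and Cox regression in general. It does not tie them to Section 10.3.4 or specify a lagged or time-varying marker.
- *The mixed model causes the inflation.* The comparison above shows otherwise.
- *First-biopsy progressors enter this analysis with a single value.* Section 3.3 treats reclassification at the baseline biopsy as a separate objective, and Section 10.3.4 does not say.

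The simulated tests also ignore the multiplicity adjustment that Section 10.5 requires. It would lower the percentages without removing the cause: at a per-test threshold of 0.01, under the 10/8/9.4/7% split with ρ = 0.5, rejection is still 22% at 0.5 SD and 84% at 1.0 SD.

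**Conclusion.** The point holds as a mismatch between question and model, together with a missing rule on the progression visit. Read in the usual way, the model of Section 10.3.4 gives no risk of progression, and nothing stops a marker without prior information from being reported as related to that risk.

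The size is an illustration. Rejection runs from about 10% to 100%, depending on the assumed shift, the timing of progression, the correlation and the effect tested. A reader might take one pair, such as 46% at 0.5 SD and about 95% at 1.0 SD, as the plan's false-positive rate. The documents give none of the inputs needed for that, and with optional blood and urine even the number of men with markers is unknown. The return to about 4-7% once the marker is lagged, or that visit dropped, is the firmer result.

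The analysis is exploratory. The primary conclusion does not depend on it, but the change is worth making before the marker data are analysed.

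**What to change.** Rewrite Section 10.3.4 as two labelled analyses.

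1. **Risk of progression.** A discrete-time hazard model (pooled logistic or complementary log-log) with a term for biopsy number. The outcome is progression at biopsy k among men still progression-free. The main predictor is the marker level at biopsy k − 1. Change up to biopsy k − 1 is a secondary predictor where two earlier values exist. Keep baseline covariates few and name them. Exclude marker values from visit k; MRI read before biopsy k may be examined as a separately stated question.
2. **Concurrent description.** Keep the mixed model, stating its response, the effect tested and the visits included. Report it as association at the time of progression, in line with Section 10.5, and not as risk or lead time.

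The cost is SAP wording; no additional data are needed. Men who progress at the first protocol biopsy do not contribute to the first analysis. Under the assumed rates about 30 of 45 events remain for lagged level and about 20 for lagged change, fewer where optional samples were refused. Intervals will be wider, and the model for change will support little adjustment, which is why level should be the main predictor.
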